6.2 Etoposide Description and Management

Brief Description: Etoposide is a topoisomerase II inhibitor that causes DNA double strand breaks and apoptosis of rapidly dividing cells, especially cancer cells. Etoposide is a common chemotherapeutic agent used in the treatment of a number of neoplasms, including lymphoma, Kaposi sarcoma, testicular cancer, Ewing sarcoma, and small cell lung cancer, among others.

Etoposide (also known as VP-16) is sold by Pfizer (New York, USA).

Full prescribing information for etoposide is available at:
https://www.pfizer.com/files/products/uspi_toposar.pdf

Dosage and Administration:

Etoposide will be administered at 100 mg/m^2 intravenous over one hour.

Storage and Stability:

Unopened vials are stable for 24 months at room temperature. Vials diluted at recommended concentration of 0.2 or 0.4 mg/ml are stable for 96 or 24 hours, respectively, at room temperature.

Handling and Disposal: Local requirements for disposal of hazardous drugs should be followed at each participating clinical site.

Please see UNC policy on hazardous drugs:

<http://intranet.unchealthcare.org/intranet/hospitaldepartments/safetynet/policies/hazardousdrugs.pdf>

6.2.1 Etoposide pharmacokinetics

After IV injection, there is a biphasic pattern of clearance with a terminal $t_{1/2}$ of about 6–8 h in patients with normal renal function. Approximately 40% of an administered dose is excreted intact in the urine. In patients with compromised renal function, dosage should be reduced in proportion to the reduction in creatinine clearance. In patients with advanced liver disease, increased toxicity may result from a low serum albumin (decreased drug binding) and elevated bilirubin (which displaces etoposide from albumin); guidelines for dose reduction in this circumstance have not been defined.

6.2.1 Adverse events associated with etoposide

The following data on adverse reactions are based on both oral and IV administration of etoposide as a single agent, using several different dose schedules for treatment of a wide variety of malignancies.

Hematologic Toxicity: Myelosuppression is dose related and dose limiting with granulocyte nadirs occurring 7 to 14 days after drug administration and platelet nadirs occurring 9 to 16 days after drug administration. Bone marrow recovery is usually complete by day 20, and no cumulative toxicity has been reported. The occurrence of acute leukemia with or without a preleukemic phase has been reported rarely in patients treated with etoposide in association with other antineoplastic agents.

Gastrointestinal Toxicity: Nausea and vomiting are the major gastrointestinal toxicities. The severity of such nausea and vomiting is generally mild to moderate with treatment discontinuation required in 1% of patients. Nausea and vomiting can usually be controlled with standard antiemetic therapy. Gastrointestinal toxicities are slightly more frequent after oral administration than after IV infusion.

Hypotension: Transient hypotension following rapid IV administration has been reported in 1% to 2% of patients. It has not been associated with cardiac toxicity or electrocardiographic changes. No delayed hypotension has been noted. To prevent this rare occurrence, it is recommended that etoposide be administered by slow IV infusion over a 30- to 60-minute period. If hypotension occurs, it usually responds to cessation of the infusion and administration of fluids or other supportive therapy

as appropriate. When restarting the infusion, a slower administration rate should be used.

Allergic Reactions: Anaphylactic-like reactions characterized by chills, fever, tachycardia, bronchospasm, dyspnea, and hypotension have been reported in 0.7% to 2% of patients receiving IV etoposide and in less than 1% of the patients treated with oral capsules. Although these reactions can be fatal, they usually respond promptly to cessation of the infusion and administration of pressor agents, corticosteroids, antihistamines, or volume expanders as appropriate. Hypertension and flushing have also been reported. Blood pressure usually normalizes within a few hours after cessation of the infusion. Anaphylactic-like reactions have occurred during the initial infusion of etoposide. Facial/tongue swelling, coughing, diaphoresis, cyanosis, tightness in throat, laryngospasm, back pain, and/or loss of consciousness have sometimes occurred in association with the above reactions. In addition, an apparent hypersensitivity-associated apnea has been reported rarely. Rash, urticaria, and/or pruritus have infrequently been reported at recommended doses. At investigational doses, a generalized pruritic erythematous maculopapular rash, consistent with perivasculitis, has been reported.

Alopecia: Reversible alopecia, sometimes progressing to total baldness, was observed in up to 66% of patients.

Other Toxicities: The following adverse reactions have been infrequently reported: aftertaste, fever, pigmentation, abdominal pain, constipation, dysphagia, transient cortical blindness, and a single report of radiation recall dermatitis. Hepatic toxicity, generally in patients receiving higher than recommended doses of the drug, has been reported with etoposide. Metabolic acidosis has also been reported in patients receiving these higher doses. The incidences of adverse reactions in **Table 6** are derived from multiple databases from studies in 2,081 patients when etoposide was used either orally or by injection as a single agent.

Table 6: Incidence of adverse events in patients receiving etoposide across multiple studies for multiple cancer types.

ADVERSE DRUG EFFECT	PERCENT RANGE OF REPORTED INCIDENCE
Hematologic toxicity	
Leukopenia (less than 1,000 WBC/mm ³)	3-17
Leukopenia (less than 4,000 WBC/mm ³)	60-91
Thrombocytopenia (less than 50,000 platelets/mm ³)	1-20
Thrombocytopenia (less than 100,000 platelets/mm ³)	22-41
Anemia	0-33
Gastrointestinal toxicity	
Nausea and vomiting	31-43
Abdominal pain	0-2
Anorexia	10-13
Diarrhea	1-13
Stomatitis	1-6
Hepatic	0-3
Alopecia	8-66
Peripheral neurotoxicity	1-2
Hypotension	1-2
Allergic reaction	1-2

7.0 CLINICAL ASSESSMENTS

Clinical assessments will be performed as outlined in the Time and Events Table in Section 8.0.

7.1.1 Concomitant Medications

All concomitant medication and concurrent therapies will be documented at baseline/screening and throughout the study as summarized in the Time and Events Table in Section 8.0. Dose, route, unit frequency of administration, and indication for administration and dates of medication will be captured.

7.1.2 Demographics

Demographic information (i.e., date of birth, gender, race) will be recorded at screening.

7.1.3 Medical History

Relevant medical history, including history of current disease, other pertinent respiratory history (e.g., tobacco use), and information regarding underlying diseases will be recorded at screening and a focused medical history of symptoms/toxicity will be performed thereafter.

7.1.4 Physical Examination

A complete physical examination including height (at screening only), weight, ECOG Performance status, lymph node assessment, and vital signs (i.e., temperature and blood pressure) will be performed by either the investigator or a sub-investigator at screening and each treatment visit.

New abnormal physical exam findings must be documented and will be followed by a physician or other qualified staff at the next scheduled visit.

7.1.5 Adverse Events

Events should be assessed per NCI-CTCAE criteria v5.0. Information regarding occurrence of AEs will be captured throughout the study. Duration (start and stop dates), severity/grade, outcome, treatment, and relation to study drug will be recorded in the eCRF. PRO-CTCAE has recently been translated and validated in Malawi and will be used to capture patient reported adverse events.

7.1.6 Clinical Disease Assessment

Response assessment varies across MCD studies, but our clinical response will be defined as follows:

Event-free survival will be defined by the absence of an event. An event includes either: relapse of symptomatic MCD requiring re-initiation of treatment as in the previous study by Bower, et al, death, or progression to non-Hodgkin lymphoma.¹⁰ Definition of symptomatic MCD for purposes of this study are the same as in the “Inclusion Criteria” (Section 4.1).

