1.5 Rationale for Clinical Study

MCD can be treated with chemotherapy. Many single-agent or combination chemotherapies have been utilized.^{7,8,29,38} However, when chemotherapy is discontinued, rapid relapses or development of NHL often occur and are associated with high mortality.^{7,8,38} Relapse after termination of chemotherapy is almost universal, and 1-year EFS is <20%.^{7,8} 15-25% of subjects treated with chemotherapy develop NHL, a rate ~15x higher than HIV-infected individuals without MCD.^{17,29,39} Survival for MCD subjects treated with traditional chemotherapy is also poor with 2-year OS of 42% in one study.⁹

Similarly, outcomes for MCD subjects treated with chemotherapy in Malawi are also poor. Of the 25 MCD patients in our cohort, 2 died before starting chemotherapy. Of 23 patients treated with chemotherapy, only 3 (13%) remain in remission after 5, 13, and 15 months respectively, similar to reports from HIC. First-line chemotherapy consisted of etoposide (17 patients) or cyclophosphamide, vincristine, and prednisone (six patients). Among 23 treated patients, 10 (43%) completed first-line chemotherapy without disease progression. The remaining 13 patients were switched to an alternative therapy because of poor response. Of the ten patients who completed first-line treatment, seven relapsed, after a median 29 days (range 14-147). One-year EFS was 10% (95% CI 2-26) (**Figure 2; Panel A**).

Rituximab has been successfully used by our group in Malawi as a compassionate-use intervention for patients with MCD refractory to chemotherapy, and in an ongoing clinical trial for diffuse large B cell lymphoma (DLBCL). As in most SSA public health systems, rituximab is not currently approved nor available in Malawi. With support from the University of North Carolina (UNC) Lineberger Comprehensive Cancer Center (LCCC), we are currently evaluating rituximab plus cyclophosphamide, vincristine, doxorubicin, and prednisone (CHOP) chemotherapy for DLBCL (NCT02660710), with 39 of 40 patients enrolled as of September 2019. To date, there have been 19 non-hematologic Grade 3 or worse AEs, and 1-year OS is 70%, which compares favorably to our previous work evaluating a historical cohort of patients treated with CHOP.⁴⁰

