3.2 Secondary Endpoints

3.2.1 At study entry, basic demographics and baseline laboratory values will be summarized using descriptive statistics (i.e., means, medians, and variability measures for continuous variable; rates and proportions for binary variables). Screening assessments to be completed within 21 days prior to study enrollment.

3.2.2 Overall survival will be assessed at 12 weeks, one year, and two years from the start of treatment.

3.2.3 Event-free survival will be defined as the rate of refractory disease, relapse (same definition of active disease as in the inclusion criteria in section 4.1), non-Hodgkin lymphoma development or death and will be assessed at 12 weeks, one year, and two years from the start of treatment.

3.2.4 Clinical response rate at end of treatment and 12 weeks from treatment initiation (clinical response defined as resolution of presenting signs/symptoms that defined

the Multicentric Castleman disease (MCD) attack) without relapse at 12 weeks. MCD attack/flare is defined in Section 4.1.1.

3.2.5 Radiologic response rate is the percentage of patients without relapse at end of treatment and 12 weeks from treatment initiation. Chest radiography and abdominal sonography will be used for staging. Per Revised response criteria for gross lymphadenopathy, response will be evaluated via complete survey of lymph nodes with measurements and physical assessment of other palpable masses with measurements.

Response criteria for lymph node response will be as follows: Complete response (CR)- disappearance of all evident disease; Partial response (PR)-at least 50% decrease in target lesions with no increase in non-target lesions, Stable disease (SD)- Neither sufficient shrinkage to qualify for PR nor sufficient increase to qualify for progressive disease (PD); PD- appearance of a new lesion or at least a 50% increase in lesion size.

3.2.6 Additional safety assessment will be graded by CTCAE v 5.0 through 12 weeks from the start of therapy.

3.2.7 Kaposi sarcoma exacerbation will be defined as new symptoms attributed to KS or clinically evident exacerbation of dermatologic or visceral disease. All disease flares will be biopsy confirmed whenever possible.

3.2.8 Quality of life will be assessed by the MCD symptom score, a patient-reported outcomes questionnaire, and PROMIS Global 10, at baseline (week 1), 15 days (week 3), end of treatment (week 5), 12 weeks, 6 months, and 24 months after treatment, and at the time of any relapse.

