10.0 STATISTICAL CONSIDERATIONS

10.1 Study Design/Study Endpoints

This is a single arm, prospective, phase II clinical trial for safety and efficacy of risk-stratified treatment with rituximab +/- chemotherapy for MCD. Eligible patients will be enrolled and treated according to the study schema. High-risk patients (defined as patients with ECOG performance status >2 or hemoglobin <8 g/dL during screening or enrollment)^{9,10,13-16} will receive four weekly doses of rituximab (375 mg/m²) and etoposide

(100 mg/m²) as in Bower, et al.⁹ Note that patients with low hemoglobin within the last month that receive a blood transfusion as treatment will be considered high risk if their pre-transfusion hemoglobin was <8 g/dL. Low-risk patients will receive the same dose of rituximab alone. The planned sample size is 27 patients and the primary outcome is safety. Secondary outcomes include one- and two-year EFS (relapse, development of NHL, or death), OS, and KS exacerbation rates. We will also collect clinical, laboratory, virologic data, and stored samples at baseline and end-of-treatment to both describe the presentation of MCD in our population and to evaluate risk factors for death or relapse. Finally, we will conduct comprehensive microcosting analysis and a Markov model cost-effectiveness analysis.

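### The EFS event list differs between sections: refractory disease, NHL and loss to follow-up each count in some places and not in others, and refractory disease has no criterion or date.

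*Combined protocol and SAP*

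**What the plan says.** EFS is described in six places in the combined protocol and SAP, and clinical response in two.

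- **7.1.6 (Clinical Disease Assessment)** opens with "our clinical response will be defined as follows". The next sentence is "Event-free survival will be defined by the absence of an event", followed by "An event includes either: relapse of symptomatic MCD requiring re-initiation of treatment", death, or progression to NHL. The section contains no response criterion.
- **3.2.3 (Secondary Endpoints)** begins "Event-free survival will be defined as the rate of refractory disease, relapse" and adds NHL and death, assessed at 12 weeks, one year and two years.
- **10.5.2**, the section that specifies the Kaplan-Meier analysis, lists relapse, refractory disease, loss to follow-up (LTFU) and death. It leaves out NHL, and its first time point is 90 days.
- **10.1** reads "Secondary outcomes include one- and two-year EFS (relapse, development of NHL, or death"; 5.1 gives the same three components.
- **1.1 (Study Synopsis)** has death, progression or NHL.
- **3.2.4** does define clinical response: "clinical response defined as resolution of presenting signs/symptoms that defined" the MCD attack, without relapse at 12 weeks.

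Objective 2.2.10 also uses the term refractory disease, asking for its predictors. The visible text gives it neither a criterion nor a date.

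**The concern.** A time-to-event endpoint needs one list of events and a date for each. Here the same patient can be an event in one section and event-free in another. The clearest case is a patient whose presenting flare never resolves. Relapse is worded as a recurrence that needs treatment to be started again, and a flare that never stopped does not plainly fit that. Unless refractory disease is an event in its own right, such a patient can stay in the event-free group until death or NHL.

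Two other outcomes are exposed in the same way: NHL without a recorded relapse, and loss of contact. A smaller problem is that a clinician who turns to the assessment section for the response criterion finds an EFS definition in its place. At stake are the EFS estimates and the predictor analysis in objective 2.2.10.

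**Working it through.** **1. The plan's own design figure.** Section 10.2 uses 24 evaluable patients, toxicity rates of 40% (null) and 20% (expected), and a rule of 6 or fewer events.

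- Exact alpha = P(X ≤ 6 | n = 24, p = 0.40) = 0.0960, below the stated 0.1.
- Power = P(X ≤ 6 | n = 24, p = 0.20) = 0.811, against the stated 80%.
- Enrolment = 24 / (1 − 0.10) = 26.7, rounded up to 27.

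The figures reproduce. None uses EFS or response, so nothing below alters them.

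**2. The event lists side by side.**

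| Section | Relapse | Refractory | NHL | Death | LTFU |
|---|---|---|---|---|---|
| 1.1 | says progression | says progression | yes | yes | no |
| 3.2.3 | yes | yes | yes | yes | no |
| 5.1 | yes | no | yes | yes | no |
| 7.1.6 | yes, if treatment restarted | no | yes | yes | no |
| 10.1 | yes | no | yes | yes | no |
| 10.5.2 | yes, if treatment restarted | yes | no | yes | yes |

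Only death is treated identically in all six. The list that drives the analysis (10.5.2) matches no other.

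**3. Three patients traced through the lists.**

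- *Flare never resolves; alive and NHL-free.* Event under 3.2.3 and 10.5.2. Not an event on the lists in 5.1, 7.1.6 and 10.1. Under 1.1, an event only if the disease is judged to have progressed.
- *NHL without a recorded relapse; alive and in contact.* Event under 1.1, 3.2.3, 5.1, 7.1.6 and 10.1. Not listed in 10.5.2.
- *In remission, then out of contact for three months.* Event under 10.5.2 only.

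**4. Size for refractory disease.** If every refractory patient is alive and NHL-free at the landmark, leaving refractory disease out raises EFS by the refractory share q. If some have died or developed NHL, the rise is smaller, so q is an upper bound. The documents give no refractory rate for first-line rituximab in this setting, so q is assumed:

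| Assumed q | Patients (27 × q) | Largest shift in EFS |
|---|---|---|
| 5% | 1.4 | 5 points |
| 10% | 2.7 | 10 points |
| 20% | 5.4 | 20 points |

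One patient is 1/27 = 3.7 points.

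**5. Timing.** Twelve weeks is 12 × 7 = 84 days. The ±7-day window in the Time and Events Table allows that visit as late as day 84 + 7 = 91, past both the 12-week landmark in 3.2.3 and the 90-day landmark in 10.5.2. An event dated at the actual visit could therefore miss the estimate it belongs to.

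**The case against.** The best defence is that the governing text already handles refractory disease. The endpoint section (3.2.3) and the analysis section (10.5.2) both count it, while 5.1 and 10.1 are one-line summaries of one- and two-year EFS. Most of this stands, and a statistician working from 10.5.2 would count these patients. But no section is said to prevail, 10.5.2 itself drops NHL, and even there refractory disease cannot be dated.

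It can also be argued that a persisting flare needing further treatment meets the 7.1.6 relapse wording, since 7.1.6 refers to the Section 4.1 criteria. That reading is possible, and its being open to argument is the reason to settle it.

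Three stronger readings are tempting and are not supported:

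- *A non-responder is scored as a responder.* A reader might infer this from the 7.1.6 lead-in. But 7.1.6 never says that absence of an EFS event is a response, and 3.2.4 requires the signs and symptoms to resolve. The likelier explanation is a missing paragraph.
- *The bias is about 10 points.* In the local salvage rituximab series (1.5), 9 of 10 patients reached remission, which suggests 10%, or 2.7 of 27. The exact 95% interval for 1/10 is about 0.3% to 45%, and these were chemotherapy-refractory patients. One patient died of MCD progression; if that was the one without remission, death is an event on every list. The 13/23 (56.5%) switched for poor response were on first-line chemotherapy and do not size an effect under rituximab.
- *The comparison with the chemotherapy cohort is invalid.* No EFS test against that cohort appears in the visible text. The stated use of historical controls is cost-effectiveness, and the cohort's EFS definition is not given.

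Finally, the clinical and lymph-node assessments are collected whichever list is used, so the data are not at risk.

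**Conclusion.** The EFS definition is internally inconsistent on refractory disease, NHL and LTFU, and refractory disease has no criterion or date. This is more than missing detail: following 7.1.6 and following 10.5.2 can give opposite classifications of the same living patient. The response problem in 7.1.6 is a drafting gap that 3.2.4 fills, not a competing definition.

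The refractory omission can raise 12-week EFS by at most the refractory share. That bound rests on assumed shares and on those patients being alive and NHL-free at the landmark. The NHL and LTFU differences are not sized, because the documents give no rate to apply. EFS and clinical response are secondary, with no sample size attached, so the point should be corrected before analysis but does not touch the primary safety conclusion.

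**What to change.** - **Response.** Put the 3.2.4 definition of clinical response under the lead-in in 7.1.6.
- **Event list.** Use one list in 1.1, 3.2.3, 5.1, 7.1.6, 10.1 and 10.5.2: refractory disease, relapse, NHL, death, and the LTFU rule as 10.5.2 now states it. Replace progression in the synopsis accordingly.
- **Refractory disease, for analysis only.** Define it as presenting signs or symptoms that never resolved by the scheduled week-12 assessment, or the start of another MCD therapy before any resolution. A patient who resolved and then had a new attack is a relapse, dated at the relapse.
- **Date.** Date refractory disease so that it counts in the first landmark despite the ±7-day window. One way is to use the start of the other therapy where there is one, and otherwise the nominal landmark day rather than the actual visit day.
- **Landmark.** Reconcile 12 weeks (3.2.3) with 90 days (10.5.2).

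The cost is protocol and SAP wording, with no new visits or data. The downside is that EFS may be slightly less favourable. The refractory definition is a proposal for classifying outcomes; the documents do not dictate it, and it sets no treatment rule.

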7.1.7 Radiologic Disease Assessment (Revised response criteria for gross lymphadenopathy)

All patients will undergo baseline on-study chest radiography and abdominal sonography for staging. Response will be evaluated via complete survey of lymph nodes with measurements and physical assessment of other palpable masses with measurements (using a flexible metric ruler in two dimensions). Chest radiography and abdominal sonography will be repeated at completion of treatment.

Measurable disease will be defined as the presence of at least one measurable pathologic lymph node or other mass that can be accurately measured by physical exam in at least one dimension with the longest diameter a minimum size of 10mm caliper measurement by clinical exam (lesions which cannot be accurately measured with calipers should be recorded as non-measurable). All measurements should be recorded in metric notation using calipers. All baseline evaluations should be performed as close as possible to the treatment start and never more than four weeks before the beginning of treatment. The same method of assessment and the same technique should be used to characterize each identified and reported lesion at baseline and during follow-up. Clinical lesions will only be considered measurable when they are superficial and ≥ 10 mm diameter as assessed using calipers.

All measurable lesions by physical exam or maximum of five lesions should be identified as target lesions and will be recorded and measured in two dimensions at baseline. Target lesions should be selected on the basis of their size (lesions with the longest diameters) and should also be those that lend themselves to reproducible

repeated measurements. A sum of the product of diameters (SPD, as in the International Harmonization Product criteria) for all target lesions will be calculated and reported as the baseline SPD. The baseline SPD will be used as reference to further characterize the objective tumor response of the measurable dimension of the disease.

All other lesions (or sites of disease), including lesions evident only by chest x-ray or ultrasound given difficulties with reproducibility of radiographic studies in our setting, should be identified as non-target lesions and should also be recorded at baseline. Measurements are not required, and these lesions should be followed as 'present' or 'absent', or in rare cases 'unequivocal progression.'

A similar strategy for response assessment based on target lesions documented by physical exam alone is currently being utilized at UNC Project Malawi for a clinical trial for lymphoma.

Response criteria for lymph node response will be as follows.

- Complete response (CR): Disappearance of all evident disease. Any pathological lymph node (LN), whether target or non-target, must have decreased to <10mm in diameter. Any non-target lesion evident by chest x-ray or ultrasound must also be documented to have resolved by repeat evaluation.
- Partial response (PR): At least a 50% decrease in SPD of up to six target lesions without any increase in size of non-target lesions.
- Stable disease (SD): Neither sufficient shrinkage to qualify for PR nor sufficient increase to qualify for PD.
- Progressive disease (PD): Appearance of a new lesion(s) >15mm in diameter, at least a 50% increase in SPD of more than one node, OR at least a 50% increase in diameter of a previously identified node >1cm. Given numerous causes of adenopathy in Malawi (particularly among HIV-infected individuals) and in order to exclude alternative non-lymphoma diagnoses, a concerted attempt to re-biopsy at the time of relapse or progression will be made unless patients refuse or the site is not amenable using locally available resources.

